6 STUDY INTERVENTION

6.1 STUDY INTERVENTION(S) ADMINISTRATION

6.1.1 STUDY INTERVENTION DESCRIPTION

Active aiTBS Intervention: We have previously discussed this stimulation approach with the FDA and the FDA deemed the approach nonsignificant risk (NSR). aiTBS will be delivered similarly to our past¹⁷²²⁰⁷ aiTBS studies using the MagVenture MagPro X100 (Skovlunde, Denmark) TMS device equipped with a Cool-B65 A/P coil. The L-DLPFC functional target will be localized for each participant using a Localite TMS Navigator (Localite, Bonn, Germany). Participants will then be treated with 1,800 pulses of iTBS (3-pulse 50-Hz bursts at 5-Hz for 2-second trains, with trains every 10 seconds) per session at 90% resting motor threshold with

depth-adjustment to the personalized functional target¹⁰³. Each session will last 10 min followed by a 50-minute intersession interval. Ten sessions will be applied per day (18,000 pulses/day) for 5 consecutive days (90,000 total pulses).

Sham aiTBS Intervention: Intervention will be administered with an 'A/P' coil (MagVenture, Denmark) which has both an active and sham side that are identical in appearance. The intervention condition is determined based on a code assigned at randomization. Based on the assigned code the magnetic stimulation is either directed towards or away from the head (i.e., when the randomization code assigns sham stimulation then the magnetic stimulation ends up being directed away from the head). During sham stimulation, however, the magnet still activates. Accordingly, the sound, appearance, and sensation of sham stimulation operation is the same as it is for active stimulation. Thus, there is no way for the operator to know if the patient is getting sham or active stimulation. Similarly, raters will have no knowledge of which ID corresponds to which intervention. This type of sham has been demonstrated to be indistinguishable from real TMS, has been well tolerated^{194,195}, and successfully used in clinical trials.

6.1.2 DOSING AND ADMINISTRATION

The goal of treatment in this study is to ensure the correct amount of treatment (90% of motor threshold) is received in the target location (L-DLPFC) rather than under-stimulating and under-treating participants. Depth correction accounts for the variable distances between the scalp and motor hotspot and scalp and treatment target from person to person. In other words, this is a personalized treatment intensity that takes into account individual variability. However, to ensure safety we never treat higher than 120% of the person's resting motor threshold, which is the standard TMS treatment intensity in routine clinical practice.

In scenarios where the cortical target depth is more superficial than the hotspot depth, the intensity will only be adjusted upwards. In no case will the stimulation be below 90% of the resting motor threshold.

Following the baseline MRI scan, participants will present to the clinic for the first of their 5-day course of aiTBS interventions (Visits 3-7). We will deliver both active and sham study intervention via a MagPro X100 (MagVenture, Skovlunde, Denmark) TMS. The intervention paradigm consists of 10 daily sessions (50 total over 5 days) of intermittent theta-burst (iTBS) stimulation (3-pulse 50-Hz bursts at 5-Hz for 2-second trains, with trains every 10 seconds), delivered with 50-minute inter-session intervals (10-minute sessions, 50-minutes in between sessions). Stimulation will be delivered at 90% of the resting motor threshold (with depth correction to account for the distance between the scalp and cortex). aiTBS protocol will be administered with a consistent dose escalation across all subjects receiving active stimulation of 18,000 pulses/day and 90,000 pulses/course. An operator entered code (derived from randomization) will instruct the device to deliver active or sham magnetic stimulation.

Custom MATLAB scripts will be used to identify the portion of the left DLPFC maximally anticorrelated with the sgACC, which will serve as the target for both active and sham stimulation. The intervention target will be located via a Localite TMS Navigator (Localite, Bonn, Germany). More specifically, the left dorsolateral prefrontal cortex is located according to routine, FDA-approved clinical rTMS practice. Our scripts then further discern functional subregions within the left DLPFC.

6.2 PREPARATION/HANDLING/STORAGE/ACCOUNTABILITY

6.2.1 ACQUISITION AND ACCOUNTABILITY

The intervention device has been purchased by the investigative team, and its use will be closely monitored by the PD and Co-I's.

6.2.2 FORMULATION, APPEARANCE, PACKAGING, AND LABELING

Because we will use the same device and coil for both active and sham study intervention (but merely change the coil side based on active or sham stimulation, as described in 6.1.1), the two study interventions will be indistinguishable.

6.2.3 PRODUCT STORAGE AND STABILITY

The study equipment will be stored in the Brain Stimulation Lab space, with routine and any additionally needed maintenance completed per manufacturer standards by the manufacturer themselves (through the purchase of a 'platinum warranty').

6.2.4 PREPARATION

The MRI, TMS, and neuronavigation devices will be used according to the manufacturer's instructions.

6.3 MEASURES TO MINIMIZE BIAS: RANDOMIZATION AND BLINDING

In this study, participants will be randomized to active vs. sham aiTBS in a 1:1 ratio in randomly selected block sizes of 2, 4, or 6 as based on a random number generator and without stratification. Blinding will be achieved via a sham rTMS coil (Cool-B65 A/P) used with the device (MagPro X100, MagVenture, Skovlunde, Denmark). This coil can deliver either active or sham iTBS in a manner that is randomized by the system itself and therefore blinded to the treater. The sham setting on this coil looks and sounds identical to the active setting but has a hidden aluminum plate blocking actual stimulation. The MagVenture TMS device holds a blinded key code that is kept by the individual that holds the blind. During the rTMS setup, the operator is instructed to flip the coil to correspond with the key code, but the operator is not able to discern the active versus sham stimulation.

For additional blinding of the operator:

- The participant wears a mouth-guard to prevent potential teeth grinding and/or audible noises from the sound of his/her mouth moving from active stimulation.
- Participants will wear headphones that generate the sound of the TMS machine as well as earmuffs to mask the actual noise of the TMS machine.
- The operator will apply lidocaine numbing gel before sessions 1, 3, 5, 7 and 9 to the scalp where the TMS coil is being placed to alleviate active stimulation discomfort.
- The operator will not touch the surface of the coil, as one side may be hotter than the other; knowing which side is hotter or colder can potentially unblind him/her.

- The operator will hang a blinding sheet/cloth over the side of the TMS coil to act as a barrier between him/her and the participant. This prevents the operator from being able to see if there are facial muscle movements, which could indicate active stimulation.

This protocol has been used to successfully blind participants in our [recent RCT](#).

The blinded randomization code will be kept in the individual case report form (CRF), and the key linking the code to the participants condition will be kept separately in an encrypted file, stored outside of the lab and able to be accessed only by a person who has no direct or indirect interaction with participants or data collection. The blind will be maintained until the completion of the study and data-lock is achieved, after which planned unblinding will take place.

Unplanned unblinding will only take place in the unlikely events that either: a) the independent DSMB requests unblinding for concerns over adverse events that are more serious / frequent than expected, or; b) on an individual basis should knowing the randomized condition for an individual participant result in improved clinical decision making in an emergency setting. In the case of unplanned unblinding, both the Stanford IRB and the Program Officer assigned to the project at NIMH will be informed.

We do not anticipate unintentional unblinding; however, in the event a member of the study team becomes unblinded, we will track this event in the CRF, and all study-team members know to not unblind other study-team members.

6.4 STUDY INTERVENTION COMPLIANCE

The study intervention is procedural in nature and, accordingly, study adherence will be directly observed. There are pre-specified places within each participant's CRF where notes to file can be logged, and we plan on documenting any missed aiTBS / MRI sessions in this location. In our experience with other investigations using aiTBS, retention is high and missed sessions are low. We subsequently do not expect to have many instances of non-adherence.

6.5 CONCOMITANT THERAPY

Participants will be required to continue all psychotropic medications throughout the study period, as they were at the time of screening. Any ongoing psychotherapy that is in a maintenance phase (i.e., not skills training) may be continued, but no new psychotherapy may be initiated during the course of the study.

To ensure adequate sleep each evening prior to TMS intervention (a safety requirement), certain sleep medications (e.g., zolpidem, zaleplon, eszopiclone, quetiapine) may be prescribed by the PD or study MD immediately prior to or during the course of TMS. These medications may be administered up to the night prior to the stimulation session (until midnight), but not during the morning of the sessions or at any time during the intervention day. The use of alternative hypnotics or the short term use of anxiolytic medications (e.g., hydroxyzine, propranolol) during an intervention day requires prior approval from the PD or study MD.

As per clinical standard of care with rTMS, participants are encouraged to bring OTC acetaminophen or ibuprofen for prophylactic use if they are concerned about the potential emergence of adverse events

that are commonly experienced with rTMS. Such use would be considered as standard of care. Short-term treatments for other headaches, mild aches/pains, or seasonal allergies will be allowed during the study provided the medications utilized have no established psychotropic effects that might confound interpretation of study outcome measures. These medications may include non-sedating, over-the-counter analgesics or antihistamines.

6.5.1 RESCUE MEDICINE

No rescue medications will be used.

7 STUDY INTERVENTION DISCONTINUATION AND PARTICIPANT DISCONTINUATION/WITHDRAWAL

7.1 DISCONTINUATION OF STUDY INTERVENTION

Discontinuation from aiTBS does not mean discontinuation from the study, and remaining study procedures will be completed as indicated by the study protocol. If a clinically significant finding is identified (including, but not limited to changes from baseline) after enrollment, the investigator or qualified designee will determine if any change in participant management is needed. Any new clinically relevant finding will be documented as an adverse event (AE), according to the AE protocol.

Discontinuation from aiTBS can be classified as temporary or permanent depending on the timing in which it occurs. If the participant has not completed visit 3 as defined in the **Section 1.3, Schedule of Activities (SoA)**, they may qualify for temporary study discontinuation. Temporary discontinuation may result from any COVID-19 related reason or other qualifying reason. This may be, but is not limited to, temporary study discontinuation while a participant quarantines or receives COVID-19 care. After receiving health clearance, they may resume the study at visit 2 if they continue to meet study criteria.

If aiTBS discontinuation occurs after the completion of visit 3, as defined in **Section 1.3 SoA**, or if a participant chooses to discontinue the study intervention, this will be classified as a permanent study discontinuation.

The data to be collected at the time of permanent study intervention discontinuation will include (if possible) the following:

- A final MRI scan (if not yet completed).
- Questionnaires about mood and well being.
- Questions about any adverse events or health problems since the last visit.

Subjects may be withdrawn from the study by the Protocol Director if a subject:

- Experiences a seizure
- Is non-adherent with study procedures
- The randomization code is broken for the subject

The Protocol Director may also withdraw a subject if he/she believes that for safety reasons it is in the best interest of the subject to be withdrawn.

Discontinuation information [e.g., date and the reason(s) for discontinuation] will be recorded in the subject's CRF (i.e., Study Completion Form) and relevant forms on REDCap.

As this is a mechanistic study, subjects withdrawn from the study may be replaced if withdrawal occurs any time prior to study completion. Should a participant fail to return for required visits or drop out of the study, effort will be made to determine why. This information will subsequently be recorded on the subject's CRF and relevant forms on REDCap.

Subjects will be encouraged to remain adherent with all expected study visits. Non-adherence to expected study visits will be documented and may result in removal from the study. This will be clearly discussed during the informed consent process and reinforced throughout the study through regular screening for issues with compliance.

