7.2 PARTICIPANT DISCONTINUATION/WITHDRAWAL FROM THE STUDY

Participants are free to withdraw from participation in the study at any time upon request.

An investigator may discontinue or withdraw a participant from the study for the following reasons:

- Pregnancy.
- Significant study intervention non-compliance.
- If any clinical adverse event (AE), laboratory abnormality, or other medical condition or situation occurs such that continued participation in the study would not be in the best interest of the participant.
- Disease progression which requires discontinuation of the study intervention.
- If the participant meets an exclusion criterion (either newly developed or not previously recognized) that precludes further study participation.
- Participant unable to receive aiTBS for the entire 5 days.
- If an incidental finding is discovered upon imaging that either the study staff (physicians) and/or CNI assigned radiologist deems unsafe or requires immediate medical followup.

The reason for participant discontinuation or withdrawal from the study will be recorded on the REDCap eCRF. Subjects who sign the informed consent form and are randomized but do not receive the study intervention may be replaced. Subjects who sign the informed consent form and are randomized and receive the study intervention and subsequently withdraw or are withdrawn or discontinued from the study before completing all required MRI scans as defined in the SoA, may be replaced.

Subjects may withdraw voluntarily from the study at any time.

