9.2 SAMPLE SIZE DETERMINATION

Sample size justification (power analysis):

Key Hypothesis of the study: A significant reduction in functional connectivity between sgACC and DMN. We hypothesize that the reduction in functional connectivity between the subgenual cingulate cortex and the default mode network from baseline to after intervention day 5 will be significantly greater for participants receiving active compared to sham aiTBS. Several past studies have found no significant changes in functional connectivity with sham rTMS targeted to DLPFC^{136,212}. Using preliminary data from our open-label study of aiTBS for treatment of severe depression, there was an effect size of 1-1.47 (depending on DMN node) for change in connectivity between sgACC and DMN¹⁵⁰. One potential approach for determining the power calculation would be that considering we will have 10 unique comparisons with each day's data be compared to every other day over 5 days, and that we will be comparing across 4 DMN nodes and 2 sgACC nodes, our target alpha needs to be $0.05/(10*4*2) = 0.000625$. Thus, for an effect size of 1, alpha of 0.000625, and a power of 0.80, and powering for an independent-measures t-test, 40 participants will be required for each arm. Regarding our secondary mechanistic endpoints, we have previously found a significant correlation between change in FC between sgACC and DMN in participants receiving open-lab aiTBS, Pearson $r = 0.51$. For a point biserial model, a two-tailed 2 test, and a power target of 0.80, 25 participants will be required for each group.

Our recruitment goals are based on our primary mechanistic endpoint. Considering a ~25% attrition rate (combined participants lost to followup and unusable or missing scans), **we plan to recruit 50 participants in each arm**, as this is larger than the 18 per arm that is required to power for a significant reduction in IMS-12, and large enough to provide sufficient power for our secondary mechanistic endpoints. Given that there are ~1,000 new depressed patients at Stanford per year, >75% are TMS-naïve, there are many more than 100 patients per year that meet inclusion criteria.

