9.4 STATISTICAL ANALYSES

9.4.1 GENERAL APPROACH

Descriptive Statistics: Categorical data will be presented as percentages. Continuous data will be presented as means with standard deviations.

Inferential tests: Statistical significance will be set at $p < 0.05$, two-tailed.

Covariates: Baseline demographic and clinical measures will be compared across intervention groups using standard statistical methods (i.e., categorical variables compared using Pearson chi square test of independence; continuous variables compared using univariate ANOVAs). Characteristics that display imbalance at the baseline measure or an association with the dependent variable will be assessed for inclusion as covariates in the final models.

Assumption checks: Continuous data will be analyzed using standard linear mixed-effects modeling in line with intent to treat analysis principles. If residuals of the standard linear models are non-normally distributed (Shapiro-Wilk), then data will be analyzed with generalized linear mixed models with Satterthwaite approximation of degrees of freedom and robust estimation of coefficients to handle violations of model assumptions. Autoregressive covariance structure will be used for all analyses except for cases in which the models fail to converge or converge on non-real solutions. In these cases, alternate covariance structures will be explored until the models converge on real solutions. All post-hoc pairwise comparisons will be Bonferroni-corrected for multiple comparisons.

General approach considerations: Primary analysis models will be reported both unadjusted and adjusted for significant clinical covariates. All statistical analysis will be conducted using SAS/STAT version 9.4 (SAS Institute Inc. 2015. SAS® 9.4 Statements: Reference, Fourth Edition. Cary, NC: SAS Institute Inc.). All statistical analyses will be overseen by our biostatistician [name], an associate professor in the Stanford department of psychiatry and behavioral sciences - Center for Interdisciplinary Brain Sciences Research. [name] holds a PhD in Applied Statistics from UCLA and is a leading expert in statistical analysis of mental health research.

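### Replacing participants who were randomised and stimulated, together with a per-protocol-only analysis, exposes the active-sham contrast to post-randomisation selection, and the replacement rule is not reconciled with the attrition allowance

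*Combined protocol and SAP*

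**What the plan says.** **Replacement.** Section 7.1 states that "subjects withdrawn from the study may be replaced if withdrawal occurs any time prior to study completion". Section 7.2 gives two narrower rules. The first is "Subjects who sign the informed consent form and are randomized but do not receive the study intervention may be replaced". The second covers those "randomized and receive the study intervention and subsequently withdraw or are withdrawn or discontinued from the study before completing all required MRI scans", who may likewise be replaced. All of this is optional.

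**Reasons for withdrawal.** The list in section 7.2 includes adverse events, inability to receive all five days of stimulation, and "Disease progression which requires discontinuation of the study intervention". Section 7.1 adds seizure and a broken randomisation code.

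**Sample size.** Section 9.2 derives 40 per arm and continues: "Considering a ~25% attrition rate (combined participants lost to followup and unusable or missing scans"; on that basis, "we plan to recruit 50 participants in each arm". It does not mention replacement. The synopsis and section 5.5 give 100 enrolled.

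**Analysis.** Section 9.3 restricts the mechanistic analyses to a per-protocol set, described only by an example (80% of the intervention on 80% of days). Section 9.4.1 describes the mixed model as "in line with intent to treat analysis principles".

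**Not stated in the text available:** a cap on replacements, which randomisation code a replacement takes, whether a replaced participant's scans stay in the analysis, and whether 100 counts people randomised or completers.

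**The concern.** The primary claim is a randomised comparison: the group-by-time interaction in section 9.4.2. Its validity depends on analysing people as randomised. Several listed reasons for leaving can depend on the arm (adverse events, not tolerating five days) or on the outcome (clinical worsening). If such people fall outside the analysis set and others who do complete fill their places, the arms that are compared are no longer the arms that were randomised. A sample restored to 50 per arm then looks complete while the selection is hidden.

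The two allowances for loss also need a stated relationship. Without one, a reader cannot tell how many people will be randomised, or whether the trial keeps its stated power if nobody is replaced.

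**Working it through.** **1. The plan's sample size (section 9.2).** Inputs: effect size 1, power 0.80, two-sided test, alpha = 0.05/(10 × 4 × 2) = 0.000625. A two-sample t-test (noncentral t) needs 39.3, so 40 per arm, with 81.1% power at 40. The plan's 40 is reproduced.

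**2. The attrition step.** 40 × 1.25 = 50 reproduces the plan's figure. To have 40 left after 25% loss the divisor is 1 − 0.25: 40/0.75 = 53.3, so 54. Since 40/50 = 0.80, 50 per arm absorbs 20% loss. At 25% loss 50 × 0.75 = 37.5 remain:

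| Evaluable per arm | Power, d = 1, alpha 0.000625 |
|---|---|
| 37 | 76.0% |
| 37.5 | 76.9% |
| 38 | 77.8% |
| 40 | 81.1% |
| 50 | 92.4% |

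**3. How the allowances overlap.** The 25% in section 9.2 covers loss to follow-up plus unusable or missing scans. Replacement reaches people who leave the study, but not someone who stays and has a bad scan. The overlap is therefore partial.

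**4. Sections 7.1 and 7.2 against each other.** Section 4.4 defines study completion as Visit 9. The last MRI is at Visit 8 (schedule of activities; section 8.1). Someone with all six scans who leaves before Visit 9 may be replaced under 7.1 but is not covered by the wording of 7.2.

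**5. Size of a selection effect (illustration; all inputs assumed).** Suppose leaving is governed by a normal latent variable that has correlation r with the change in connectivity, and the fraction q at one end leaves. Those who remain are shifted by r × m(q) SD, where m(q) = φ(z_q)/(1 − q). The shift in the active-sham difference is r × [m(q_sham) − m(q_active)].

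- m(0.05) = 0.1031/0.95 = 0.109
- m(0.10) = 0.1755/0.90 = 0.195
- m(0.25) = 0.3178/0.75 = 0.424
- m(0.30) = 0.3477/0.70 = 0.497

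Smallest case (25% v 10%, r = 0.2): 0.2 × (0.424 − 0.195) = 0.046 SD. Largest case (30% v 5%, r = 0.5): 0.5 × (0.497 − 0.109) = 0.194 SD.

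**6. What replacement adds.** The formula has no replacement term, because a replacement who completes comes from the same selected population. Only the standard error changes. In the largest case, for a simple two-group comparison at two-sided 5%:

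- No replacement: 35 sham and 47.5 active remain. SE = √(1/35 + 1/47.5) = 0.223, bias/SE = 0.87, false-positive rate about 14%.
- Replacement to 50 completers per arm: SE = √(2/50) = 0.200, bias/SE = 0.97, false-positive rate about 16%.

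In the smallest case both are between 5% and 6%. Replacement leaves the bias where it was and makes it slightly more likely to reach significance.

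**The case against.** **The cause lies elsewhere.** Most of the selection comes from section 9.3. A per-protocol-only set selects participants whether or not anyone is replaced. A reader might infer that replacement by itself turns the trial into a comparison of completers. The documents do not support that: they nowhere say that replaced participants' scans are discarded. Section 7.1 says that stopping stimulation is not leaving the study, and seeks a final MRI. The 80% example could also retain someone who stopped late. This objection stands. Replacement would do little harm if every stimulated participant stayed in the model.

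**Attrition is not simply counted twice.** That reading is tempting, but the 25% includes scan losses that replacement does not reach, replacement is discretionary, and 50 per arm does not fully cover 25% anyway. A reader might also infer that about 134 people will be randomised (50/0.75 = 66.7, so 67 per arm). That would follow only if all the loss were withdrawal and all of it were replaced up to 50 completers, which no section says.

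**Losses may be small.** Section 2.2 reports one drop-out among 31 over the five-day course, and section 6.4 expects few missed sessions. The first figure is open-label and says nothing about sham. The differential loss in step 5 has no support in the documents and serves only to show scale.

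**Codes and arm balance.** Taking the next code from the blocked list is the ordinary reading of section 6.3, and nothing suggests arm-matched replacement. The protocol need only say so.

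**Power.** The shortfall is measured at the sizing alpha of 0.000625. Section 9.4.2 tests the interaction at 0.05, where a simple t-test with 37.5 per arm has 80% power for about 0.66 SD. The shortfall is therefore against the plan's own sizing criterion and does not threaten the primary test.

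**Conclusion.** The concern holds in a limited form. The plan permits discretionary replacement of people already randomised and stimulated, including those who leave for reasons that may depend on arm or outcome. It carries a separate attrition allowance that overlaps with this in part, and it does not reconcile the two. The per-protocol-only set conflicts with the stated intent-to-treat principles and is the main route to selection. Replacement compounds it and makes it less visible.

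On the assumed inputs the completer contrast shifts by about 0.05-0.19 SD under no true effect. That is modest beside the design effect of 1 SD, but enough to raise the false-positive rate. If losses are few or similar in the two arms, the shift is close to nil. Separately, and from the plan's own inputs, 50 per arm covers 20% loss; at 25% loss power is about 77% against the 80% target. This last figure counts anyone lost as contributing nothing, so it is somewhat pessimistic for a mixed model that keeps partial scan sets.

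The point should be settled before database lock, but is not fatal to the design.

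**What to change.** 1. Limit replacement to people randomised but never stimulated, with the replacement taking the next randomisation code. Reconcile sections 7.1 and 7.2 to this single rule.
2. Amend section 9.3 so that the primary mixed model includes every stimulated participant with all usable scans, whether or not the course or the scan series was completed. Keep the per-protocol set as a supportive analysis, with a definition specific to this five-day course. This also brings section 9.3 into line with section 9.4.1.
3. State that 100 counts randomised participants, apart from replacements for those never stimulated.
4. Restate section 9.2: either an allowance of 20% with 50 per arm, or 25% with about 77% power at alpha 0.000625. If 80% at 25% loss is wanted, 54 per arm is needed, which is 8 more participants in total.
5. Report withdrawals, with reasons, and replacements by arm.

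**Cost.** A protocol amendment, with a real change to the analysis population in section 9.3 as well as to wording. There will be fewer complete six-scan sets than with open replacement, and the stated power will look slightly less favourable unless the extra 8 participants are recruited.
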